****CONFIDENTIAL & PROPRIETARY****

13.3	Membership	24
13.4	DSMB Meetings	24
13.5	Reports to the DSMB	25
13.6	Documentation of DSMB Meetings	26
13.7	Confidentiality and Objectivity	26
14.	Statistical Considerations	26
14.1	Data Analysis Plan	27
14.2	Sample Size	27
15.	Risks and Benefits	27
15.1	Risks to Subjects	27
15.2	Potential Benefits to Subjects	27
16.	Privacy & Confidentiality	27
16.1	Data collection	28
16.2	Data Storage	28
16.3	Biospecimens	28
17.	Ethical Considerations	28
17.1	Regulatory Authority Approval	28
17.2	Ethics Approval	29
17.3	Conflict of Interest	29
18.	Publications	30
19.	References	30

List of Abbreviations and Definition of Terms

AE	Adverse Events
BPH	Benign Prostatic Hyperplasia
BRB	Biomedical Research Building
CNS	Central Nervous System
CRF	Case Report Form
CTCAE	Common Terminology Criteria for Adverse Events
eCRF	Electronic Case Report Form
ED	Erectile Dysfunction
EDITS	Erectile Dysfunction Inventory of Treatment Satisfaction
EDV	End Diastolic Velocity
GCP	Good Clinical Practice
HIPAA	Health Information Portability and Accountability Act
ICF	Informed Consent Form
ICH	International Conference of Harmonization
ICI	Intracavernosal Injection
IEC	Institutional Ethics Committee
IIEF	International Index of Erectile Function
IIEF-EF	Erectile Function Subdomain Score
IPSS	International Prostate Symptom Score
IRB	Institutional Review Board
ISCI	Interdisciplinary Stem Cell Institute
MCID	Minimal Clinically Important Difference
mL	Milliliter
ng/dL	Nanograms Per Deciliter
PDE5i	Phosphodiesterase 5 inhibitor
PPP	Platelet Poor Plasma
PRFM	Platelet Rich Fibrin Matrix
PRP	Platelet Rich Plasma
PSV	Peak Systolic Velocity
RCT	Randomized Controlled Trial
SAE	Serious Adverse Events
SGA	Subject Global Assessment
SOP	Standard Operating Procedure
SWT	Low-intensity Shockwave Therapy
TE-SAE	Treatment Emergent Serious Adverse Events
UM	University of Miami
VAS	Visual Analogue Pain Scale

Protocol Synopsis	
TITLE	Novel Treatment for Erectile Dysfunction C ombining S hockwave T herapy and P latelet R ich P lasma (COCKTAIL)
SPONSOR	Desai Sethi Urology Institute, University of Miami, Miller School of Medicine
PHASE OF STUDY	Phase I/II
STUDY THERAPY	Autologous Platelet-Rich Plasma (PRP) + Low-intensity Shockwave Therapy (SWT)
STUDY DESIGN	Randomized, Double Blind, Placebo Controlled, Pilot Trial
ROUTE OF ADMINISTRATION	Intracavernosal Injection (PRP) + extracorporeal shockwave therapy (SWT)
SUBJECT POPULATION	60 male subjects between the age of 30-75 with Mild or Mild-to-Moderate ED
STUDY OBJECTIVES	
Primary: To investigate and compare the treatment efficacy of PRP injection + SWT vs placebo injection / SHAM treatment in men with mild-moderate ED, as measured by IIEF.
 
Secondary: To study incidence of adverse events and safety of PRP injection + SWT treatment in men with mild-moderate ED, as measured by IIEF.

INVESTIGATION PLAN	
60 men with Erectile Dysfunction (ED) of organic origin, that meet all of the inclusion and none of the exclusion criteria, will be randomized to receive either PRP+SWT, or placebo/sham in a 1:1 double-blinded fashion.
 
a) Group A (30 subjects): Autologous PRP injection + SWT therapy. All subjects in this group will receive 2 sessions of autologous PRP penile injection with 30 ± 7 day treatment interval. 5mL of PRP will be injected at each session. Additionally, patients will receive a total of 3600 shocks over a five-week period, starting at initial PRP injection.
 
b) Group B (30 subjects): Placebo (Normal Saline) + SHAM. All subjects in this group will receive 2 sessions of normal saline penile injection with 30 ± 7 day treatment interval. 5mL of normal saline will be injected at each session. Additionally, patients will receive SHAM treatment over a five-week period, starting at initial placebo injection.

DURATION OF STUDY	7 months (1 month screening, 5 weeks of therapy sessions, 6 months of follow-up).
DEFINITION OF ENDPOINTS	
Primary:
 
 - Incidence of treatment emergent serious adverse events (TE-SAEs) in all patients during the study period. 
Secondary:
 
 - Change in IIEF-EF score from baseline to 3 and 6 months post-therapy compared to control group. - Percentage of subjects that achieve minimal clinically important difference (MCID) in IIEF-EF from baseline to 3 and 6 months post-therapy compared to control group, - Percentage of subjects who either decrease or discontinue use of PDE5i after three months post-therapy compared to control group. 
Exploratory:
 
 - Differences in Doppler ultrasound parameters (PSV and EDV) from baseline to 6 months post-therapy compared to control group. - Treatment satisfaction as assessed by EDITS questionnaire in all subjects. -

Protocol Synopsis	
INCLUSION CRITERIA	
 1. Be Male 2. Be 30 to 80 years of age (inclusive). 3. Be able to provide written informed consent. 4. Have a diagnosis of mild to moderate ED (12-21) or mild ED (22-25) based on IIEF-EF questionnaire score. 5. Be in a stable heterosexual relationship, and have a minimum of 2 sexual attempts per month for at least one month prior to enrollment. 6. Agree to comply with all study related tests/procedures.
EXCLUSION CRITERIA	
 1. Previous penile surgery of any kind (except circumcision and condyloma removal), such as penile lengthening, penile cancer surgery, penile plication, grafting. 2. Previous history of priapism, penile fracture, Peyronie's Disease, or penile curvature that negatively influences sexual activity, 3. Abnormal morning serum testosterone level defined as a value lower than 300 ng/dL ($\pm 5\%$). 4. Psychogenic ED as determined by study investigator. 5. Patients using ICI for management of ED 6. Patients with generalized polyneuropathy, neurological conditions, or psychiatric disease (such as bipolar disorder or depression). 7. Have a serious comorbid illness or condition that, in the opinion of the investigator, may compromise the safety or compliance of the subject or preclude successful completion of the study. 8. History of consistent treatment failure with PDE5 inhibitors for therapy of ED. 9. Poorly controlled diabetes as indicated by Hemoglobin a1c > 9%. 10. Use of antiplatelet medication

1. Protocol Title

Novel Treatment for Erectile Dysfunction Combining Shockwave Therapy and Platelet Rich Plasma (The COCKTAIL Clinical Trial)

2. Background

2.1 Platelet-based therapies

Platelet-derived therapies are a growing trend across multiple medical and surgical specialties including dermatology, ophthalmology, cardiology, colorectal surgery, plastic surgery and mainly orthopedics [1-2]. One of the most well described platelet-based therapies is autologous platelet-rich plasma (PRP) [3]. PRP is derived from the centrifugation of whole blood with a separator gel to remove the red and white blood cells. The resulting supernatant has a greater than four-fold increase in platelets and other plasma proteins [1]. This concentrate is then administered via injection. PRP has been frequently used for orthopedic conditions such as bone and soft tissue trauma, inflammatory conditions, and chronic pain syndromes [3-4]. Evidence suggests that platelets play an important role not only in coagulation but also in regulation of body metabolism, promotion of the wound healing, tissue regeneration, vascular remodeling and inflammatory/immune responses through secretion of growth factors, cytokines and chemokines [4-5]. These biologically active proteins include transforming growth factor- β , platelet-derived growth factor, platelet-derived epithelial growth factor, insulin-like growth factor, vascular endothelial growth factor, basic fibroblast growth factor, as well as many others [6]. When platelets are activated, they release these growth differentiation factors, facilitating even nerve repair and regeneration [7-8]. Growth factors act locally and are implicated in many aspects of natural wound healing, including chemotaxis, cell proliferation, cell differentiation and angiogenesis. They also control and conduct synthesis, modification and degeneration of extracellular matrix proteins. Coordination of these cellular and molecular processes is integral to proper wound healing and tissue regeneration [9]. The key role of platelets in these processes makes them an attractive candidate for therapies aimed at accelerating natural healing, as well as tissue regeneration.

Autologous blood-based biomaterials are promising therapeutic options for varied pathology. Rapid generation of therapeutic material following collection allows for point-of-care therapy [10]. Furthermore, an autologous therapy avoids the need for immunosuppression and eliminates concerns of rejection. Newer strategies to prolong the anti-inflammatory and wound healing properties of platelets have focused on creating a fibrin matrix (platelet rich fibrin matrix, PRFM) to bind the platelets and prevent extravasation from the site of injection, thereby addressing the concern of early washout with PRP [11]. In addition, PRFM offers a potential scaffold for tissue ingrowth and may allow continued release of platelet-related factors for a longer duration. Across multiple disciplines, PRP has been used both as a primary treatment modality and as a supplement to other therapies in hopes of supplementing wound healing, tissue regeneration, and angiogenesis. Although most of the studies focusing on PRP injections have been relatively small and heterogenous, they largely support the concept of administration in terms of safety, while efficacy remains uncertain. Finally, the concept of

autologous therapy has been shown in the real world that it is particularly attractive to patients [10].

2.2 Platelet-rich plasma treatment for erectile dysfunction

Erectile dysfunction (ED) affects as many as 1 in 4 men, and evidence indicates that incidence is rising [12-13]. The pathophysiology is multifactorial, but the most common pathophysiology, vasculogenic erectile dysfunction, has as first sign endothelial dysfunction secondary to inflammation [14]. The most common treatments for ED aim to improve endothelial function through augmentation of the nitric oxide pathway [15]. Return of potency after surgical injury of CNS partially depends on axon regeneration in the remaining neural tissue [16]. The process of regeneration and functional recovery of peripheral nerve is slow and is influenced by many factors [17] such as extracellular matrix, neurotrophic factors, and cellular components [18]. Recent advances in the understanding of molecular pathways and their physiological role demonstrate that growth factors are an important part of the development, maintenance, and regeneration of the nervous system [19]. Various growth factor neuromodulatory strategies, including insulin-like growth factor (IGF-I) and neurotrophic factors, are investigated to identify agents that may have neuroprotective and regenerative function after the occurrence of peripheral nerve injury. Accumulating evidence indicates that neuroimmunophilin ligand (such as FK506) plays a significant role in neural regeneration and upregulation of neuronal nitric oxide synthase (nNOS), as well as in the recovery of erectile function after CN injury occurrence [20-21]. FK506 neuroprotection after CN injury is mediated by antioxidative/nitrosative and anti-apoptotic pathway [22]. When platelets are activated, they release many kinds of growth differentiation factors and a few types have been found to facilitate nerve repair and regeneration. Moreover, corporeal dysfunction due to smooth muscle atrophy or other intracavernosal pathology can lead to corporo-venous occlusive erectile dysfunction despite a normal arterial inflow. Rejuvenating the Corporeal tissues with PRP, which is well known for its growth and healing factors, is a possible modality as a potential treatment for erectile dysfunction according to Alkhayal et al [23]. In their retrospective study examining the efficacy of one intra-cavernosal PRP injection to 40 ED patients, they reported that mean IIEF-5 score before treatment was 13 (5-20) and post treatment IIEF-5 = 17 (7-24), ($p < 0.001$). Other studies have shown similar results with minimal side effects, no serious adverse reactions and potential efficacy (Table 1) [23-26].

Human Studies of PRP for ED							
Author	Year	Number of Patients	Patient Population	Administration	Followup	Adverse Events	Conclusion
Banno [26]	2017	N=9	Penile Rehab	PRP ICI into Pnies with Vacuum Device	4 weeks	No AEs reported	PRP may represent a safe and viable option as a supplementary therapy for penile rehabilitation. Particularly notable is the prospect of zero side effects.
Matz [24]	2018	N=16	Erectile dysfunction, Peyronies Disease	PRP with CaCl ICI	15.5m	Minor: Bruising 1, Mild Pain 4. Major: none	PRFM injections for ED, PD, and female SUI are feasible and safe. Although the limited data is suggestive of efficacy, a placebo control will be required in subsequent efforts for confirmation
Epifanova [25]	2019	N=10	Erectile Dysfunction	6 injections PRP with CaCl2 ans Shockwave	60 Days	No AEs reported	There were no serious adverse events as well as severe adverse events. Erectile dysfunction symptoms in all men participated in the study significantly decreased after treatment with PRP-therapy and extracorporeal shockwave therapy
Alkhayal [23]	2018	N=40	Erectile Dysfunction	1 injection PRP	> 1 month	No AEs reported	Platelet rich plasma is a safe and efficacious option for penile rejuvenation and improvement of erectile dysfunction

Table 1: Summary of published studies and abstracts

To date, there are no treatments that address the underlying cause of endothelial dysfunction, although LIST treatment for ED has shown promising results. Platelet-derived therapies targeting inflammation and promoting tissue/nerve regeneration and may represent a potential treatment option towards this direction. Despite growing evidence to the efficacy of PRP, no randomized placebo-controlled studies exist.

2.3 Energy-based treatments for erectile dysfunction

Shockwave therapy has been utilized by urologists for other ailments, such as treatment of kidney stones through a non-invasive manner. Interest in the use of low-intensity shockwave therapy for erectile dysfunction was augmented with success seen in preclinical models. The hypothesis for SWT's mechanistic actions is neo-angiogenesis, recruitment of progenitor cells and resident stem cells, improvement of microcirculation, vasodilation with subsequent increase in nitric oxide, decrease in fibrosis, and nerve regeneration. There have been 13 published clinical studies regarding use of SWT for ED. Multiple systematic reviews and meta-analyses have been performed for SWT for ED, and there is consensus that SWT shows promise in the treatment for ED.

2.4 Combination Restorative Therapy for Erectile Dysfunction

The development of ED therapeutics that focus on neurovascular regeneration and repair strategies are of great importance. A large body of *pre-clinical* work has demonstrated the effect of SWT alone (monotherapy) on angiogenesis and progenitor / stem cell recruitment for ED [2, 3, 8-11]. PRP monotherapy importantly is also supported by well-defined mechanistic insights obtained from rigorously conducted animal studies [12-19]. All the previous studies in humans have evaluated either IIEF scores and / or penile Doppler ultrasound hemodynamic parameters, but there has not been evaluation of the treatment as a combination. The proposed mechanisms of both interventions would

suggest that the combination therapy would act in a synergistic manner, with superiority over monotherapy. Success of our proposed work could fundamentally change the standard of care for ED and substantially improve the quality of life for tens of millions of men.

3. Study Objectives

3.1 Primary Objective:

To investigate and compare the safety of PRP and SWT vs placebo/sham treatment in men with mild-moderate ED.

3.2 Secondary Objective:

To study the treatment efficacy of PRP and SWT treatment vs placebo/sham treatment in men with mild-moderate ED.

4. Study Endpoints

4.1 Primary Endpoint (safety):

- Incidence of treatment emergent serious adverse events (TE-SAEs) in all patients during the study period. Adverse events will be recorded at every visit. The following contains a list of the anticipated adverse events:
 - Pain
 - Bruising
 - Swelling
 - Edema
 - Allergy
 - Penile Fracture
 - New Penile Curvature

4.2 Secondary Endpoints (efficacy):

- Change in IIEF-EF score from baseline to 3 and 6 months post-therapy compared to control group.
- Percentage of subjects that achieve minimal clinically important difference (MCID) in IIEF-EF from baseline to 3 and 6 months post-therapy compared to control group,
- Percentage of subjects who either decrease or discontinue use of PDE5i after three months post-therapy compared to control group.

4.3 Exploratory Endpoints:

- Differences in Doppler ultrasound parameters (PSV and EDV) from baseline to 6 months post-therapy compared to control group.
- Treatment satisfaction as assessed by EDITS questionnaire in all subjects.
- Changes in IPSS questionnaire between treatment and control group.
- Perceptions of therapeutic allocation between treatment and control group.

5. Study Location

The study will be funded by the NIH (R01DK130991-01) and coordinated by the University of Miami (UM), Miller School of Medicine, Desai Sethi Urology Institute. The UM Interdisciplinary Stem Cell Institute (ISCI) will also support the project (logistics, quality control, management, storage of specimens and data). All study visits will be carried out in the Desai Sethi Urology Institute clinics, (Address: [name], University of Miami Miller School of Medicine, Miami, FL) or Christine Lynn Rehabilitation Center (Address: [name]).

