5.1 Additional Study Sites

No additional study sites.

6. Study Population

60 males with ED of organic origin. All patients will be regular PDE5i users/responders. Men with ED will be evaluated by IIEF-EF domain and eligible patients will be randomized to one of 2 treatment groups with an equal allocation ratio (1:1). Participants who do not meet eligibility criteria will be considered a screen failure and will not receive the study therapy.

6.1 Inclusion criteria:

In order to participate in this study, a patient must:

- 1) Be Male
- 2) Be 30 to 80 years of age (inclusive).
- 3) Be able to provide written informed consent.
- 4) Have a diagnosis of mild to moderate ED (12-21) or mild ED (22-25) based on IIEF-EF questionnaire score.
- 5) Be in a stable heterosexual relationship, and have a minimum of 2 sexual attempts per month for at least one month prior to enrollment..
- 6) Agree to comply with all study related tests/procedures.

6.2 Exclusion criteria:

In order to participate in this study, a patient must not have any of the following:

- 1) Previous penile surgery of any kind (except circumcision and condyloma removal), such as penile lengthening, penile cancer surgery, penile plication, grafting.
- 2) Previous history of priapism, penile fracture, Peyronie's Disease, or penile curvature that negatively influences sexual activity,
- 3) Abnormal morning serum testosterone level defined as a value lower than 300 ng/dL ($\pm 5\%$).
- 4) Psychogenic ED as determined by study investigator.
- 5) Patients using ICI for management of ED
- 6) Patients with generalized polyneuropathy, neurological conditions, or psychiatric disease (such as bipolar disorder or depression).

- 7) Have a serious comorbid illness or condition that, in the opinion of the investigator, may compromise the safety or compliance of the subject or preclude successful completion of the study.
- 8) History of consistent treatment failure with PDE5 inhibitors for therapy of ED.
- 9) Poorly controlled diabetes as indicated by Hemoglobin a1c > 9%.
- 10) Use of antiplatelet medication

7. Identification and Enrollment of Subjects

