7.4 Withdrawal Criteria

All subjects who either screen fails, is withdrawn from the study, or has completed all visits should be de-enrolled from the research database within 2 business days, in accordance with university policies (or respective institutional policy).

Subjects may be withdrawn from the study for any of the following reasons:

- a) A subject does not meet the eligibility criteria (the subject will be considered a screen failure).
- b) A subject withdraws consent.
- c) If a new treatment for erectile dysfunction is made available during the study duration, the investigator will inform the patient at a follow-up visit, and be offered withdrawal to utilize new treatment.
- d) A subject expires during protocol participation from causes other than the study treatment (not due to adverse events).
- e) At the discretion of the principal investigator for issues of non-compliance, or other behavioral factors.

8. Procedures Involved

60 men with Erectile Dysfunction (ED) of organic origin, that meet all of the inclusion and none of the exclusion criteria, will be randomized to receive either PRP+SWT, or placebo/sham in a 1:1 double-blinded fashion.

- a) Group A (30 subjects): Autologous PRP injection + SWT therapy. All subjects in this group will receive 2 sessions of autologous PRP penile injection with 30 ± 7 day treatment interval. 5mL of PRP will be injected at each session. Additionally, patients will receive a total of 3600 shocks over a five-week period, starting at initial PRP injection.
- b) Group B (30 subjects): Placebo (Normal Saline) + SHAM. All subjects in this group will receive 2 sessions of normal saline penile injection with 30 ± 7 day treatment interval. 5mL of normal saline will be injected at each session. Additionally, patients will receive SHAM treatment over a five-week period, starting at initial placebo injection.

8.1 Schedule of Events:

The events table for the conduct of this study is shown below:

Table 1:

Schedule of Events		Screening	Treatment					Follow Up	
Time Point		0-30 days before randomization	Week 1	Week 2	Week 3	Week 4	Week 5	Month 3	Month 6
Event			Day 0	Day 7 \pm 2	Day 14 \pm 2	Day 21 \pm 2	Day 28 \pm 2	Day 90 \pm 14	Day 180 \pm 14
Informed Consent		X							
Demographics		X							
Medical History		X							
Physical Exam		X							
Doppler Ultrasound		X							X
Questionnaires	IIEF	X						X	X
	EDITS							X	X
	VAS		X	X	X	X	X		
	IPSS	X							X
	SGA								X
Laboratory Tests		X							

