- 8.2.13 *PRP/Placebo Injection:*** Approximately 120mL of blood will be collected from participants for preparation of investigational product. Refer to Section 9.2 for description of IP preparation and administration.

8.2.14 Concomitant Medications: Review of current use of prescription and over the counter (OTC) medications. Participants must discontinue use of PDE5i medications throughout the duration of the study.

8.2.15 Review Adverse Events: Refer to Section 12 for description and reporting of adverse and serious adverse events.

8.2.16 SWT/Sham Treatment: In the treatment group, patients randomized will receive 5 weekly sessions, in which 720 shocks of treatment energy will be applied in every session to each treated region (left and right corpora cavernosa and crura). In the sham group, patients will have the same number of sessions, and the machine will be set to deliver 720 shock treatments, but the machine will not fire shockwaves.

8.2.17 Laboratory Testing: Hematology, chemistry, hemoglobin A1C, and serum testosterone lab test results will be collected at screening. If any standard of care labs testing have been performed within 12 months of the date of the screening visit, those results may be used for the purpose of this study.

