8.3.3 Follow Up Visits: Months 3 and 6 Post-Treatment

Follow up visits will occur within 90 ± 14 days (Month 3) and 180 ± 14 days (Month 6) days after final treatment visit. Refer to table 1 for procedures to be performed at the follow up visits visit.

9. Investigational Product

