14.1 Data Analysis Plan

Analysis plan: Continuous data will be analyzed using ANOVA with repeated measures, or student's T-Test (where applicable) in order to compare differences between the treatment and control groups. For categorical data, Fisher's Exact test to determine differences between groups. Statistical significance will be evaluated using $\alpha=0.05$.

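### The secondary endpoint on reducing or stopping PDE5i cannot separate the arms, because the protocol requires every man to stop PDE5i for the whole study

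*Combined protocol and SAP*

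**What the plan says.** The third secondary efficacy endpoint in Section 4.2, repeated in the synopsis, is "Percentage of subjects who either decrease or discontinue use of PDE5i after three months post-therapy compared to control group".

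Four other places bear on it:

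- **Section 6 (Study Population):** "All patients will be regular PDE5i users/responders".
- **Section 8.2.14 (Concomitant Medications):** "Participants must discontinue use of PDE5i medications throughout the duration of the study". The sentence applies to both arms and has no exception.
- **Synopsis, Duration of Study:** "7 months (1 month screening, 5 weeks of therapy sessions, 6 months of follow-up". Follow-up is part of the study. Section 8.3.3 places both later visits there: "Follow up visits will occur within 90 ± 14 days (Month 3) and 180 ± 14 days (Month 6) days after final treatment visit".
- **Section 7.4(e):** a man may be withdrawn "At the discretion of the principal investigator for issues of non-compliance, or other behavioral factors".

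PDE5i use is captured only through the concomitant-medication item in 8.2.14: "Review of current use of prescription and over the counter (OTC) medications". The schedule in Section 8.1 has this review at every visit. Section 14.1 assigns categorical outcomes to Fisher's test ("Exact test to determine differences between groups") at α = 0.05.

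**The concern.** The endpoint treats coming off PDE5i as something the therapy might bring about. Section 8.2.14 makes it a condition of taking part. A man who obeys the protocol has therefore met the endpoint in either arm, however his erections respond.

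The secondary objective is efficacy, and this is one of its three endpoints. As written, the trial would report either a flat 100% in both arms or a difference made up of men who broke a protocol rule, some of whom the investigator may have withdrawn under 7.4(e). A reader could take the first as evidence of no effect and the second as evidence of benefit, and neither reading would be sound.

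**Working it through.** The plan gives no expected rate, power or sample size for this endpoint, so there is no figure of its own to reproduce. The check has a logical step and then a numerical one.

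**Step 1. The sections side by side.**

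| Element | Source | Consequence |
|---|---|---|
| All men use PDE5i regularly | Section 6 | Everyone has use to stop |
| All men must stop, both arms, whole study | 8.2.14 | Everyone who complies has stopped |
| Study includes 6 months of follow-up | Synopsis | The ban covers Months 3 and 6 |
| Success = decreased or stopped | 4.2 | Every man who complies is a success |

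No section limits the ban to the treatment weeks, lets use restart, provides rescue use, or says how a decrease is measured.

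**Step 2. Result if 8.2.14 is followed.** Inputs: 30 men per arm, or 24 after the 20% attrition assumed in Section 14.2 (30 × 0.8 = 24).

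- 30/30 against 30/30: difference 0, Fisher p = 1.
- 24/24 against 24/24: difference 0, Fisher p = 1.
- If the reference were use at Day 0, after the mandated stop, nobody could decrease: 0% against 0%, again p = 1.

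The probability of a significant result is zero in each case.

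**Step 3. How much rule-breaking would produce a difference.** A man fails the endpoint only if he resumes at or above his earlier use; resuming at a lower level still counts as a decrease. With no failures on active and k on control, n per arm, the two-sided Fisher p-value is

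p = 2 × C(n, k) / C(2n, k).

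- n = 30, k = 5: 2 × 142,506 / 5,461,512 = 0.052.
- n = 30, k = 6: 2 × 593,775 / 50,063,860 = 0.024.
- n = 24, k = 4: p = 0.109.
- n = 24, k = 5: 2 × 42,504 / 1,712,304 = 0.0496.

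So at least 6 of 30, or 5 of 24, control men must be back at full use while no active man is.

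**Step 4. Chance of p < 0.05 at 30 per arm.** The documents give no resumption rate, so these rates are assumptions. With none on active, the chance is P(X ≥ 6) for X ~ Binomial(30, q), where q is the control rate:

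- q = 5%: 0.3%.
- q = 10%: 7.3%.
- q = 20%: 57.2%.

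Zero resumption on active is the most favourable case. With 20% on control, the chance falls to about 24% if 5% resume on active, and to about 10% if 10% do.

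**The case against.** The contradiction itself is hard to dispute. The best case on the other side concerns how far it reaches.

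- **Rule-breaking may carry signal.** The trial is randomized and double-blind, and both arms face the same ban. Men whose erections improve have less reason to break it, so more resumption on control could partly reflect a treatment effect. This stands as a caution against calling such a difference meaningless. It would still be insensitive, mixed up with adherence, and exposed to withdrawals under 7.4(e).
- **The 100% figure needs more than compliance.** Current PDE5i use is in the description of the population in Section 6 but not among the inclusion criteria in 6.1. A man not using PDE5i could be enrolled under the listed criteria and could then neither decrease nor stop. The endpoint also names no reference period. Both points are fair, and the 100% is conditional on them. Neither restores a contrast that treatment could move.
- **The ban may have been drafted too broadly.** The endpoint's timing, after three months post-therapy, may mean that use was expected to be free from then on. No section says so, and Month 6 lies inside the study. If that was the intent, 8.2.14 is the text that needs correcting.
- **The scenarios are illustrative.** They are, and 57% is the most favourable case for its control rate. The conclusion rests on Steps 1 and 2, not on them.

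**Conclusion.** The concern holds. Followed as written, the endpoint is 100% in both arms with p = 1, whatever the treatment effect. This assumes that Section 6 is accurate in calling all men regular users, that 8.2.14 is obeyed, and that stopping is judged against pre-study use. If the rule is not obeyed, any difference comes from deviations and cannot be read as efficacy in the way the endpoint intends.

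The defect is confined to one of three secondary efficacy endpoints. The primary endpoint (treatment-emergent serious adverse events) and the sample size, which rests on MCID responders, are untouched. It should be fixed before analysis.

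**What to change.** The sponsor has to decide which rule applies; this is a clinical choice.

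1. **If the ban stands:** remove the endpoint from the synopsis and Section 4.2. Report by arm the proportion of men taking any PDE5i, from the concomitant-medication review, as a protocol deviation. This is a wording change that needs no new data and loses one nominal secondary endpoint.
2. **If PDE5i was meant to be allowed in follow-up:** rewrite 8.2.14 to say from when, define the endpoint against use recorded at screening, and state how a decrease is measured (dose, frequency or tablets). This changes trial conduct. Men could be on PDE5i when IIEF-EF is measured at Months 3 and 6, which affects the other two secondary endpoints. Lifting the ban only after the Month 3 visit would limit that to Month 6.
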